80 from women attending cervical cancer screening (1, 2). To date, there is no Swiss available
81 data about the impact of HPV vaccination. The earlier sign of HPV vaccination could
82 probably be observed on the HPV prevalence and precursor lesion in women population. To
83 date, there is no Swiss available data about the impact of HPV vaccination. The earlier sign
84 of HPV vaccination could probably be observed on the HPV prevalence and precursor lesion
85 in women population. An observational study conducted in Australia support that the
86 incidence of genital warts decreases in younger women (3-5). Another trial conducted in
87 England (6) has showed that the national HPV immunization program seemed successful in
88 preventing HPV 16/18 infection in sexually active young women. The prevalence of HPV
89 16/18 infection in the post-immunization survey was 6.5% amongst 16–18 year olds,
90 compared to 19.1% in the similar survey conducted prior to the introduction of HPV
91 immunization.

92 In USA, the US population-based sentinel surveillance system to monitor HPV impact show
93 that from 2008 to 2012, prevalence of HPV 16/18 in CIN2+ lesions statistically significantly
94 decreased from 53.6% to 28.4% among women who received at least one dose HPV vaccine
95 (*P*_{trend}<.001) but not among unvaccinated women (57.1% vs 52.5%; *P*_{trend}=.08) or women
96 with unknown vaccination status (55.0% vs 50.5%; *P*_{trend}=.71) (7). More recently, a
97 systematic review and meta-analysis describe that, in countries with female vaccination
98 coverage of at least 50%, HPV type 16 and 18 infections decreased significantly between the
99 pre-vaccination and post-vaccination periods by 68% (RR 0.32, 95% CI 0.19-0.52) and
100 anogenital warts decreased significantly by 61% (RR 0.39, 0.22-0.71) in girls 13-19 years of

101 age. Comparing to countries with female vaccination coverage lower than 50%, significant
102 reductions in HPV types 16 and 18 infection (RR 0.50, 95% CI 0.34-0.74]) and in anogenital
103 warts (0.86 [95% CI 0.79-0.94]) occurred in girls younger than 20 years of age, with no
104 indication of cross-protection or herd effects (8).

105 To evaluate the effectiveness of this vaccination, it is important to detect quickly,
106 economically and efficiently prevalence of HPV high risk in our population. In Switzerland,
107 young women who want to get tested do either with their gynecologists or so via

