108 gynecological hospital visits. This method is certainly effective, but expensive, furthermore
109 screening coverage is still insufficient (only 30 to 40 % women's don't participate at the
110 screening) in Switzerland. Also a part of our study population don't participate in screening
111 such young people of foreign origin for various reasons, no gynecological medicine,
112 economic cost etc ...

113 Several studies raise the effectiveness and efficiency (9) of the self sampling to increase
114 screening coverage (10), participation rate of nonattenders (11, 12) self-sampling has been
115 nearly as sensitive as clinician-obtained cervical samples and more sensitive than cytology
116 for the detection of cervical intraepithelial neoplasia (CIN) for lesions of high-grade CIN-II or
117 higher (CIN-II+) (13-14) .

118 Through this study we want to evaluate the possibility of using self sampling as a screening
119 tool in a real population, yet a study in Geneva showed the possibility of its use for screening
120 a population not visiting gynecological hospital visits (15), but the actual population use
121 remains to be demonstrated.

122 **2. Objectives**

123 Through this study, we evaluate the possibility to use self sampling as a screening tool in a
124 real population, document the effectiveness of this vaccination on the prevalence of HPV
125 infections and assess evolution of infection and we will assess the evolution of viral
126 infection and clearance of throughout 5 years in a population of young, unvaccinated and
127 vaccinated girls.

128

129 **Primary objective**

- 130 • Explored the feasibility of establishing a home-based Self-HPV screening strategy in
131 general population

132

133 **Secondary objective**

- 134 • To determine the HPV prevalence of vaccine-type: 19 high-risk HPV types (16, 18, 26,
135 31, 33, 35, 39, 45, 51, 52, 53, 56, 58, 59, 66, 68, 69, 73, 82) and 9 low-risk HPV types(6,

136 11, 40, 42, 43, 44, 54, 61, 70) in young women population attending High schools in
137 Geneva and Faculty of Medicine at the University of Geneva.

138 • To generate data about vaccination impact and vaccine coverage.

139

140 • To assess the infection's evolution and clearance of HPV throughout 5 years in a
141 population of young, unvaccinated and vaccinated young women

142

143

144 **3. Material and method**

145

146 ***Inclusion criteria:***

147 • Eligible women aged between 18-31 years attending of Haute Ecole de Santé –

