148 Genève and Faculty of Medicine at the University of Geneva.

149 • Understands study procedures and accepts voluntarily to participate by signing the
150 informed consent form (ICF)

151

152 ***Exclusion criteria:***

153 • History of hysterectomy or treatment on the cervix during the last 12 months.

154

155

156 **Study Design and Methods**

157

158 Setting: The study will be conducted in collaboration with the High school of health in Geneva
159 and Faculty of Medicine at the University of Geneva. The study will be proposed to 400
160 women attending these schools.

161

162 Recruitment: It will take place in the health school of health and Faculty of Medicine at the
163 University of Geneva. Trial information on the University website will be available; it will also
164 contain a phone number for helpline. Cards to check eligibility, registration and scheduling
165 will be available. The HPV self-collection kit will be directly distributed to participants at the
166 end of their courses to School of Health and University of Geneva School of Medicine

167

168 Data collection: Vaccination status, age, menopausal status, marital status, parity, tobacco
169 consumption, medical records, geographic data, consulting-date and HPV-test result.

170

171 HPV tests: The HPV self-collection kit included a dacron swab, collection tube, instructions
172 with explanatory pictures, consent forms and a participant demographic information. The

173 HPV analysis will be performed by Real-time PCR. Delay between sampling and lab
174 processing will be noted.

175

176 Technical aspect: Written informed consent will be obtained by papier. All women will
177 perform a self sampling for HPV testing using a simple swab with no medium. The results of
178 HPV testing and sociodemographic data will be archived in a database.

179

180 Statistical analysis: The expected vaccination coverage in this population is about 50%.
181 According vaccination status, 2 different groups will be formed (vaccinated vs non-
182 vaccinated). The cases of HPV infection (status HPV+) will then be calculated for each group
183 and compared according to the vaccination status. The applied statistical tests will be
184 McNemar's test for comparison.

185

186 Sample size: Sample size was obtained based on estimated prevalence of 6% of HPV 16/18
187 infection in the Swiss population aged less than 30 years. A total of 200 specimens per group

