188 would be needed to detect about an 85% reduction in HPV 16/18 prevalence (prevalence of
189 0.9% in the vaccinated population), given an 80% power and a two-sided significance level of
190 95% (based on representative data from England). We therefore estimate that a sample size
191 of 400 women (200 in each group) will be adequate for the analyses.

192

193 Follow up: Participants will receive their results by e-mail directly via our colposcopy nurse.
194 We will follow the HPV-positive participants every 6 months during 5 years to assess the
195 evolution of their HPV status and the viral clearance. In order to do this, every 6 months they
196 will receive a self-sampling HPV kit at home, which they will return by mail to the
197 HUG for analysis.

198

199

200 **4. Statement regarding the relevance and potential contribution of the project to** 201 **cancer control**

202 Data from the registries will be used to assess the HPV prevalence of the pre-vaccine era
203 and will be the basis for monitoring infection after post-vaccine introduction. This study will
204 provide important data about the prevalence of HPV infection in a young and sexually active
205 population of women and on the proportion of vaccinated and non-vaccinated young women.

206 Despite the impact of vaccine on invasive cancers is not expected until some decades after
207 its extensive implementation, as the type-specific prevalence of HPV infection is very high in

208 young sexually active populations, the effect of a successful HPV vaccination program
209 should be quickly detected by sentinel surveillance in this sub-population.

210 Monitoring the impact of the vaccination programs by detecting type-specific infection is
211 important as it is the earliest anticipated change, and failure to detect protection from
212 infection will indicate failure to prevent cancer in the subsequent decades and allow the
213 implementation of appropriate changes in cervical cancer screening strategies.

214 This surveillance is required in order to document the expected gains in cancer prevention if
215 there is appropriate population coverage. In our case, no data is available in Switzerland.
216 Such surveillance would allow further studies to determine the duration of protection, long-
217 term safety and actual impact on health-care cost consumption.

218 In this project, 400 young girls will know their statuses for HPV infection and will obtain

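### The single crude HPV-positive contrast by vaccination status does not separate a vaccine effect from a difference in HPV exposure, and the 28-type result that could help is given no role

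*Protocol*

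**What the plan says.** The Statistical analysis paragraph (Protocol, section 3) forms two groups from existing vaccination status, with about 50% expected to be vaccinated. It continues: "The cases of HPV infection (status HPV+) will then be calculated for each group", and the two counts are compared with McNemar's test. No randomisation, matching, adjustment or type-specific contrast is named.

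The Sample size paragraph works with a narrower outcome: "Sample size was obtained based on estimated prevalence of 6% of HPV 16/18" in women under 30, against 0.9% in the vaccinated, which gives 200 per group.

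The first secondary objective (section 2) reads "To determine the HPV prevalence of vaccine-type: 19 high-risk HPV types (16, 18, 26" and goes on to list 28 types in all, 6 and 11 among them, under the one label vaccine-type. The vaccine or vaccines used are not named.

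Data collection (section 3) lists vaccination status, age, menopausal and marital status, parity, tobacco, medical records, geography, date and HPV result. It lists no sexual-behaviour or partner item.

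Section 2 sets out to show how effective vaccination is against HPV prevalence. Section 4 treats a failure to see protection as a sign that cancer will not be prevented.

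**The concern.** A causal conclusion is to be drawn from a crude comparison of women who were or were not vaccinated for reasons outside the study. If vaccinated women simply have less exposure to HPV of every type, their prevalence is lower with no contribution from the vaccine, and the stated contrast would count this as effectiveness.

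An imbalance is foreseeable from the protocol itself. The programme began in 2008 at ages 11 to 14, with catch-up at 15 to 19. Women aged 28 to 31 at the protocol date in 2016 were 20 to 23 in 2008, above both ranges, so vaccination is tied to age. (The Background also puts the catch-up group at age 32 in 2015, which does not fit those ranges. The age link is therefore used here only as a reason to expect imbalance, and enters no figure.)

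With no sexual-behaviour item listed, later modelling cannot adjust directly for the route of exposure. The typing result partly fills that gap. Types that the vaccine does not affect should differ between groups only through exposure. The contrast as written instead merges them with 16/18 in one positive/negative status.

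**Working it through.** **Inputs from the protocol.** 200 per group; HPV 16/18 prevalence 6% in the unvaccinated and 0.9% in the vaccinated; 80% power; two-sided. The significance level is printed as 95% and is read here as 5%. Types: 19 + 9 = 28, of which 28 − 2 = 26 are not 16/18.

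**Assumptions, not in the protocol.** Other-type prevalence q in the unvaccinated is 10%, 20% or 30%. One exposure ratio r (vaccinated to unvaccinated) applies to all types. 16/18 and other-type infections are independent within a group. The other types are unaffected by vaccination. The tests are Pearson tests for independent groups, since no pairing that McNemar's test could use is described.

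**Step 1: the plan's own figure.** With p̄ = (0.06 + 0.009)/2 = 0.0345,

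n = [1.96·√(2·0.0345·0.9655) + 0.842·√(0.06·0.94 + 0.009·0.991)]² / (0.06 − 0.009)² = (0.506 + 0.215)² / 0.0026 ≈ 200.

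The stated 200 per group reproduces. Power by this approximation is 80.0%; enumerating the Pearson test exactly gives 85%. The arithmetic of the sample size is not at issue.

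**Step 2: 16/18 comparison with no vaccine effect.** Prevalence in the vaccinated is 0.06·r. The exact probability of a significant result is:

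| r | vaccinated prevalence | apparent reduction | P(significant) |
|---|---|---|---|
| 0.8 | 4.8% | 20% | 8% |
| 0.7 | 4.2% | 30% | 12% |
| 0.6 | 3.6% | 40% | 20% |
| 0.5 | 3.0% | 50% | 30% |

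**Step 3: the any-HPV contrast as written, no vaccine effect, r = 0.7.** Positivity is 1 − (1 − 0.06)(1 − q) in the unvaccinated and 1 − (1 − 0.042)(1 − 0.7q) in the vaccinated. For q = 20% this is 24.8% against 17.6%. Simulation with 200,000 replicates per setting gives the last column:

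| q | unvaccinated | vaccinated | P(significant) |
|---|---|---|---|
| 10% | 15.4% | 10.9% | 26% |
| 20% | 24.8% | 17.6% | 42% |
| 30% | 34.2% | 24.3% | 59% |

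With equal exposure and the planned 85% reduction in 16/18, the same contrast has power of only about 27%, 16% and 12%. At q of 20% or 30% it is thus more likely to reach significance through a 30% exposure difference than through the planned vaccine effect.

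**Step 4: 16/18 infections against other-type-only infections.** Among infected women, the share with 16/18 is compared by vaccination status. With no vaccine effect, r = 0.7 and q = 20%, the shares are 0.06/0.248 = 24.2% and 0.042/0.176 = 23.9%, so the exposure difference almost cancels. The simulated rejection rate is about 5% for every q. With equal exposure and a true 85% reduction, power is 74%, 80% and 82% for q = 10%, 20% and 30%, against 85% for the direct 16/18 test.

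**Step 5: what the control types can show.** If r = 0.6 and the true reduction is 85%, the crude 16/18 ratio is 0.15·0.6 = 0.09, the control-type ratio is 0.60, and 0.09/0.60 = 0.15 recovers the vaccine effect. Precision is limited. The 95% CI of the control ratio extends by a factor exp(1.96·√(2(1 − q)/(200q))) either way, which is 1.80, 1.48 and 1.35. The chance that the control comparison itself is significant at r = 0.7 is about 18%, 36% and 54 to 55%.

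**The case against.** **It could be left to the SAP.** Supporting analyses are ordinary SAP content, the type results will be archived, and nothing rules the extra tables out. That is fair for missing detail. But the protocol does state an analysis, and that analysis does not serve its effectiveness aim. The choice of target and control types is also worth most if made before results are seen.

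**The quoted sentence plans no 16/18 contrast.** Correct: it compares any HPV positivity. This makes matters worse (Step 3), and the outcome has to be set to 16/18 before a control-type analysis has a place.

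**All 26 other types as controls.** A reader might infer that every type except 16/18 is a ready control. The documents do not support this. Types 6 and 11 are among the 26, the Background reports falls in anogenital warts after vaccination, a cited reference concerns a quadrivalent vaccine, and the vaccine used is not named. The Background's remark that no cross-protection was seen concerns countries with coverage below 50%, while about 50% is expected here. Subtracting the difference seen in all 26 types could remove real vaccine effect.

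**The control is weak.** This stands. A moderate imbalance would often be missed (Step 5).

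**Effectiveness is not the primary objective.** True; feasibility of self-sampling is. This limits the weight of the point but does not remove it, because the whole sample size rests on the vaccination contrast.

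**Conclusion.** The point holds in a limited form: the stated analysis does not separate vaccine effect from exposure difference, and the typing data could help to do so. For 30% less exposure and no vaccine effect, false significance is about 12% for a 16/18 comparison and about 26% to 59% for the any-HPV contrast as written. It is near 5% when 16/18 infections are set against other-type-only infections.

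These figures rest on 200 per group, 6% HPV 16/18, an assumed other-type prevalence of 10% to 30%, one exposure ratio for all types, and independence between types.

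A reader might infer that a 16/18 difference in this study could never be told apart from selection. That goes too far. Type results and some covariates (age, marital status, parity, tobacco) are recorded, so a better analysis remains possible. For confounding alone to look like the planned 85% reduction, the exposure ratio would have to be 0.15. Moderate differences are the vulnerable ones.

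**What to change.** Change the Statistical analysis paragraph as follows.

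- Make the vaccinated/unvaccinated comparison for HPV 16/18, the outcome on which the sample size rests, with a test for independent groups.
- Supporting analysis 1: the same comparison for a prespecified set of control types. Exclude every type targeted by the vaccines used (for example 6 and 11, if a vaccine covering them was used) and any type for which cross-protection is expected. Report the 16/18 and control-type prevalence ratios side by side with CIs.
- Supporting analysis 2: an indirect-cohort comparison of 16/18 infections against control-type-only infections by vaccination status.

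The cost is two tabulations, a short list of types and a few sentences; no new data are needed. The paragraph should state three limits. The type-controlled analysis has somewhat less power (about 74% to 82% against 85% for a true 85% reduction). Its estimate is conservative if cross-protection exists. The control comparison detects 30% less exposure only about 18% to 55% of the time, so a null control result must not be read as proof of equal exposure. A narrower control set lowers q and moves both ranges towards their lower ends.

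### The sample-size paragraph prints the two-sided significance level as 95%, which is the confidence level; 200 per group is reproduced at 5%

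*Protocol*

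**What the plan says.** The Sample size paragraph in section 3 (Material and method) starts from an HPV 16/18 prevalence of 6%, described as that of "infection in the Swiss population aged less than 30 years. A total of 200 specimens per group". It continues that this number "would be needed to detect about an 85% reduction in HPV 16/18 prevalence (prevalence of" and then "0.9% in the vaccinated population), given an 80% power and a two-sided significance level of". The next line supplies the level: "95% (based on representative data from England). We therefore estimate that a sample size". The total is 400 women, 200 in each group.

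The sentence runs on without a gap or redaction, so the 95% is what the protocol prints as its significance level. Neither the Abstract nor the Statistical analysis paragraph gives a significance level for this study. The Statistical analysis paragraph names McNemar's test but no alpha.

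**The concern.** A significance level is the probability of rejecting a true null hypothesis. A level of 95% would mean declaring a difference in 95 of 100 studies in which vaccination made none. The figure is evidently the complement of the intended level, that is, the confidence level.

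This sentence is the document's only statement of a type I error threshold. Anyone who takes the threshold for the vaccinated against unvaccinated comparison from the protocol, or who tries to re-derive the sample size from its stated inputs, meets a value that cannot be used. At stake is the correctness of a stated design parameter. The number of women to recruit is not in question.

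**Working it through.** **Inputs, all from the Sample size paragraph**
- Prevalence in the comparison group: p1 = 0.06.
- Prevalence in the vaccinated group: p2 = 0.009. Check: 1 − 0.009/0.06 = 0.85, which agrees with the stated reduction of about 85%.
- Power 80%, so z = 0.8416.
- Two-sided test, equal groups, 200 per group stated.

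**Step 1. Reproduce 200 per group at two-sided 5%.** The pooled two-proportion formula without continuity correction is

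n = [z(1−α/2) · √(2·p̄·(1−p̄)) + z(power) · √(p1(1−p1) + p2(1−p2))]² / (p1 − p2)²

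- p̄ = (0.06 + 0.009)/2 = 0.0345, and √(2 × 0.0345 × 0.9655) = √0.06662 = 0.2581.
- √(0.06 × 0.94 + 0.009 × 0.991) = √0.065319 = 0.2556.
- n = (1.960 × 0.2581 + 0.8416 × 0.2556)² / 0.051² = (0.5059 + 0.2151)² / 0.002601 = 199.85.

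Rounded up, this is the stated 200. By the same formula, power at 200 per group is 80.0%.

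**Step 2. How firmly does this identify 5%?** The protocol does not name its formula, so other readings were tried.

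| Two-sided level | Formula | n per group |
|---|---|---|
| 5% | pooled, uncorrected | 199.85 |
| 5% | unpooled | 197.1 |
| 5% | arcsine | 168.8 |
| 5% | pooled, continuity-corrected | 237.4 |
| 10% | pooled, uncorrected | 157.3 |
| 10% | pooled, continuity-corrected | 194.5 |
| 1% | pooled, uncorrected | 297.7 |

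The standard formula at the conventional level gives 200 on rounding up. A level of 10% with a continuity correction comes near but does not give it.

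**Step 3. What would a literal 95% imply?** The critical value is z(1 − 0.475) = 0.0627, so the test rejects almost whatever the data show. A two-sided test rejects in either tail, and at this level both tails count. Under the same normal model:

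| n per group | Tail in the expected direction | Opposite tail | Total power |
|---|---|---|---|
| 1 | 0.554 | 0.396 | 0.950 |
| 2 | 0.587 | 0.365 | 0.951 |
| 21 | 0.803 | 0.164 | 0.967 |
| 200 | 0.997 | 0.002 | 0.999 |

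Power starts at about 95% and rises from there. No group size gives 80%, so 95% and 80% power cannot both be design inputs.

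**Step 4. What does the 80% refer to?** The expected numbers of positives are small: 200 × 0.06 = 12 and 200 × 0.009 = 1.8. The normal approximation and the exact power therefore differ. Summing over the two binomial distributions at 200 per group and two-sided 5% gives:
- uncorrected chi-square test (identical to the pooled z-test): 85.1%;
- Fisher's exact test: 76.5%.

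The 80.0% in step 1 is thus the pooled normal approximation and not the exact power of either test.

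**The case against.** The strongest reply is that this is a familiar slip with no consequence. Interchanging 95% confidence and 5% significance is common, most readers will correct it silently, and the arithmetic behind 200 per group is sound. All of that stands, and it sets the weight of the point. It does not make the printed text right, and nothing elsewhere in the document corrects it. Nor can it be left to a statistical analysis plan, since the protocol does state the level and states it wrongly.

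Four stronger readings are tempting and are not supported:
- **That a literal 95% would need only about 21 per group.** The usual formula does return 20.6, but it counts rejections in one tail only. That is harmless at 5% and wrong at 95%: with both tails, power at 21 per group is 96.7%, not 80%.
- **That the sample size is miscalculated or the study underpowered.** The stated inputs reproduce 200. Fisher's test and the continuity correction ask for more, but the sample-size paragraph does not claim to use either.
- **That the 80% is the true power of an uncorrected z-test.** That test is the uncorrected chi-square test, whose exact power is 85.1%.
- **That the England data contradict the 85%.** The Background reports a fall from 19.1% to 6.5%, which is 1 − 6.5/19.1 = 66%. That is a population change before and after the programme, not a contrast of vaccinated with unvaccinated women, so it neither yields nor refutes 85%.

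The choice of McNemar's test for two independent groups is a separate matter and adds no weight here.

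**Conclusion.** The significance level is wrong as written. The protocol's own inputs match two-sided 5% (199.85, rounded up to 200 per group), and the printed 95% is incompatible with 80% power at any group size.

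Two assumptions lie behind this. First, because the formula is not named, 5% is inferred as the level that reproduces 200 by the standard formula and by convention; it is not proved to be the only possible reading. Second, the statement about power at a literal 95% rests on the normal model that underlies the size formula; at very small group sizes that model is only a rough description of counts.

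The point is minor. The sample size stands, few readers would be misled, and the vaccinated against unvaccinated comparison serves a secondary objective, the primary one being the feasibility of home-based self-sampling.

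**What to change.** In the Sample size paragraph, replace 95% with 5% as the two-sided significance level. Keep 400 women, 200 per group.

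Naming a method for the 80% is optional. If one is named, the text should say that the power is 80.0% by the pooled normal approximation, and not present it as the exact power of a particular test. If exact figures are wanted beside it, they are 85.1% (uncorrected chi-square) and 76.5% (Fisher's exact test) at 200 per group and two-sided 5%.

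The cost is one changed figure and, optionally, one added clause. Recruitment, groups and data collection are unaffected.
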